9.2.2. ARAT Response

The test is scored for left and right side separately.

Performance on each item is rated on a 4-point ordinal scale ranging from:

- 3 - Performs test normally in less than 5 seconds
- 2 - Completes test, but takes abnormally long or has great difficulty, with time varying from 5 to 60 seconds
- 1 - Performs test partially
- 0 - Can perform no part of test

Subjects who achieve a maximum score on the first (most difficult) item are credited with having scored 3 on all subsequent items on that scale. If the subject scores less than 3 on the first item, then the second item is assessed. This is the easiest item, and if subjects score 0 then they are unlikely to achieve a score above 0 for the remainder of the items and are credited with a zero for the other items.

The ARAT is a 19 item measure divided into 4 sub-tests

1. Grasp subscale with 6 items and a score range of 0-18,
2. Grip subscale with 4 items and a score range of 0-12,
3. Pinch subscale with 6 items and a score range of 0-18, and
4. Gross arm movement subscale with 3 items and a score range of 0-9

The maximum score on the ARAT is 57 points (possible range 0 to 57) for each side.

The proportion of SB623 treated subjects (pooling both SB623 doses) and sham that improve at least 6 points from baseline on the ARAT total score at the affected side will be compared to sham-surgery controls at each timepoint using a GLMM model that will include treatment, visit, treatment-by-visit, baseline ARAT total score at the affected side, baseline MRS score and pooled surgical site. The analysis will be repeated by the comparisons of each SB623 group versus sham control for each visit. Summary tables for actual total scores and the change from baseline values will be provided. Mean change from baseline of the ARAT total scores at the affected side using the same MMRM model

Statistical Analysis Plan

as specified in Section 9.1.2 for FMMS will be provided as well for the comparison of combined SB623 versus sham control and separately for the comparisons of each SB623 group versus sham control for each visit.

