9.1.2. FMMS Score - Additional Analysis

An additional analysis using mixed model for repeated measures (MMRM) will be performed treating the change from baseline in FMMS motor total score as a continuous outcome (dependent) variable. The independent variables will be treatment, visit, treatment-by-visit interaction, and pooled surgical site as effects, and baseline FMMS motor total score and baseline mRS score as covariates. Treatment, visit, and pooled surgical site will be treated as categorical variables. Visit will be fitted as a repeated effect within subject. The analysis will be carried out using a restricted maximum likelihood (REML) based repeated measures approach. An unstructured variance-

Statistical Analysis Plan

covariance matrix will be used. If this fails to converge then the following variance-covariance structures will be used based on the step-down order until model convergence is obtained: heterogeneous Toeplitz, heterogeneous autoregressive, heterogeneous compound symmetry, and then compound symmetry. The Kenward-Roger method will be used to estimate the denominator degrees of freedom. Means and least-squares means (LS-mean) by treatment group and visit, along with the SE of LS-mean for the change from baseline measurement will also be displayed. Treatment comparisons will be displayed showing the treatment difference LS-mean and the 95% confidence limits of the treatment differences along with the p-value for the comparison of combined SB623 versus sham control and separately for the comparisons of each SB623 group versus sham control for each visit. Significance tests will be based on LS Means using Type III sum of squares

These additional analyses for FMMS motor total score will be repeated for the UE-FMMS and LE-FMMS subscale scores indicated in Section 9.1.1

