9.2.3. Gait Velocity

Gait Velocity is measured on a standard 10 m walk. Two trials will be tested. The average results from the two trials will be used for analysis. A single trial result will be used if the result of one of the two trials result is missing. If physical support is needed, the velocity will be set as missing. The proportion of SB623 treated subjects that improve at least 1 functional level (e.g. from <0.4 m/s to 0.4-0.8 m/s or from 0.4-0.8 m/s to >0.8 m/s) from baseline on Gait Velocity will be compared to sham-surgery controls at each time point using a similar GLMM model to the primary efficacy analysis. The GLMM model will include treatment (SB623 combined doses vs. sham surgical control), assistive device use (yes/no), visit, treatment-by-visit, baseline gait velocity score, baseline mRS score and pooled surgical site as fixed effects. The analysis will be repeated by the comparisons of each SB623 group versus sham control for each visit.

Summary tables for actual and change from baseline in gait velocity score will be provided. The mean change from baseline in gait velocity score will be analyzed using the same MMRM model as specified in Section 9.1.2 for FMMS will be provided as well with assistive device use (yes/no) included as a covariate. In addition, for each treatment group, a shift table of frequencies and percentages will be presented summarizing changes in walk time status (< 300 seconds vs. \geq 300 seconds) from Baseline to each post-baseline visit. McNemar's Test will be used to test the null hypothesis that the true probability of a walk time < 300 seconds is equal at Baseline and the post-baseline visit.

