21	32.2	2.1	38	48.6	3.3
22	33.0	2.1	39	51.2	3.8
23	33.7	2.0	40	58.6	6.4
24	34.5	2.1			

A score can be approximated if a participant skips a question before calculating the T-score. If items are missing, first check how many items were answered. For short forms with at least 5 items, confirm that 4 or 50% of items, whichever is greater, have been answered. For example, a 4-item short form can only be scored with complete data. A 10-item short form can be scored as long as the participant answered at least 5 items. After confirming that enough responses were provided, sum the response scores from the items that were answered. Multiply this sum by the total number of items in the short form. Finally, divide by the number of items that were answered. For example, if a respondent answered 5 of 8 questions and answered all items with the second lowest response option (2), you would sum all responses (10), multiply by the number of items in the short form (8) and divide by the number of items that were actually answered (5). Here $(10 \times 8) / 5 = 16$. If the result is a fraction, round up to the nearest whole number. This is a prorated raw score. However, this prorated score should be used with caution as the advantages of Item Response Theory (IRT) calibrations and their contribution to precision is lost in the process.

The mean score change from baseline in the two subdomain (Upper extremity function and Lower extremity function) for the T scores of SB623 treated subjects (individually

Statistical Analysis Plan

by treatment group and for both groups combined) will be compared to sham-surgery controls at each timepoint using a mixed model for repeated measures model (MMRM).

Restricted maximum likelihood MMRM model will include treatment, visit, pooled site, corresponding baseline subdomain T score, baseline mRS score, and the treatment-by-visit interaction. The same step-down procedure described in Section 9.1.1 will be used if the unstructured covariance matrix used in the model does not converge. Missing observations will not be imputed for this analysis. Least square mean differences and 95% CIs will be presented for SB623 treatment individual and combined groups versus sham control.

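### The ARAT and gait velocity change-from-baseline MMRMs inherit baseline FMMS as their covariate if read literally, and do not name the baseline of the score analysed

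*SAP*

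**What the plan says.** SAP 9.1.2 sets out the MMRM for change in FMMS motor total score. Its effects are treatment, visit, their interaction and pooled surgical site, with "baseline FMMS motor total score and baseline mRS score as covariates".

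Two later sections import that model by reference:

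- **ARAT (SAP 9.2.2):** "Mean change from baseline of the ARAT total scores at the affected side using the same MMRM model", continuing "as specified in Section 9.1.2 for FMMS will be provided as well for the comparison of combined SB623 versus sham control". No covariate is restated.
- **Gait velocity (SAP 9.2.3):** "The mean change from baseline in gait velocity score will be analyzed using the same MMRM model as specified in Section 9.1.2 for FMMS". The one stated modification is "with assistive device use (yes/no) included as a covariate".

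For the FMMS subscales, SAP 9.1.2 says only this: "These additional analyses for FMMS motor total score will be repeated for the UE-FMMS and LE-FMMS subscale scores".

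Where the SAP writes a model out in full, it names the baseline of the outcome. The ARAT responder GLMM lists baseline affected-side ARAT, the gait responder GLMM lists baseline gait velocity, and the NeuroQOL MMRM lists "corresponding baseline subdomain T score, baseline mRS score".

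The sample MMRM code in Appendix I has a generic change outcome and a single baseline term that is not defined. SAP Section 12 lists the change-from-baseline MMRMs for FMMS, ARAT and gait velocity among exploratory analyses added to those in the protocol.

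**The concern.** A programmer who follows the cross-reference literally would adjust change in ARAT, or change in gait velocity, for baseline FMMS and baseline mRS, and not for the outcome's own baseline. For a change score, the own baseline is usually the covariate that explains most variance, and it is already collected. Leaving it out gives a less precise treatment difference. Any chance imbalance in that baseline is then removed only as far as baseline FMMS happens to track it.

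The text also allows two programmers to fit different models and so report different differences, intervals and p-values in Tables 14.2.3.2 and 14.2.4.2. The covariate should be fixed before unblinding.

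**Working it through.** **1. What the text fixes.** The plan gives no figure to reproduce here, so the first step is to set the sections side by side.

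| Analysis | Baseline covariates named | Own baseline named? |
|---|---|---|
| FMMS change MMRM (9.1.2) | FMMS total, mRS | Yes |
| ARAT responder GLMM (9.2.2) | affected-side ARAT, mRS | Yes |
| ARAT change MMRM (9.2.2) | by reference to 9.1.2 | No |
| Gait responder GLMM (9.2.3) | gait velocity, mRS | Yes |
| Gait change MMRM (9.2.3) | by reference to 9.1.2, plus assistive device use | No |
| NeuroQOL MMRM (9.2.4) | own subdomain T score, mRS | Yes |
| Appendix I MMRM code | one undefined baseline term, no mRS | Open |

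**2. Cost in precision.** The documents give no correlations, so these are assumptions. Let rho be the correlation of a score's baseline with its follow-up value, and r the correlation of that baseline with baseline FMMS. Take equal variances (set to 1) at a single visit. Assume baseline FMMS relates to follow-up only through the own baseline, and ignore baseline mRS, which is in both models.

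- Residual variance of change, adjusted for own baseline: 1 − rho²
- Residual variance of change, adjusted for baseline FMMS: 2(1 − rho) − r²(1 − rho)²
- Ratio of the second to the first: [2 − r²(1 − rho)] / (1 + rho)

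Interval width grows as the square root of the ratio.

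| rho | r | Ratio | Width factor |
|---|---|---|---|
| 0.9 | 0.8 | (2 − 0.064)/1.9 = 1.019 | 1.009 |
| 0.8 | 0.6 | (2 − 0.072)/1.8 = 1.071 | 1.035 |
| 0.7 | 0.4 | (2 − 0.048)/1.7 = 1.148 | 1.072 |

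The upper limit at rho = 0.7, with r = 0, is 2/1.7 = 1.176.

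**3. Chance imbalance.** With the planned 104 treated and 52 sham subjects (SAP 3.5), the standard error of a baseline difference is √(1/104 + 1/52) = 0.17 SD. Imbalance up to 1.96 × 0.17 = 0.33 SD is therefore within ordinary 95% limits. If baseline FMMS is adjusted for instead of the own baseline, the part expected to remain in the treatment difference is (1 − rho)(1 − r²) times the imbalance:

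- rho 0.9, r 0.8: 0.036 × 0.33 = 0.01 SD
- rho 0.8, r 0.6: 0.128 × 0.33 = 0.04 SD
- rho 0.7, r 0.4: 0.252 × 0.33 = 0.08 SD

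This is not a second loss on top of step 2. The extra residual variance there equals (1 − rho)²(1 − r²), which is the variance of this same unremoved component.

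**4. UE- and LE-FMMS.** The FMMS total is the sum of the two subscales (66 + 34 = 100 points), so it contains each subscale's baseline and r should be high. At an assumed r of 0.9 the ratio is 1.034, 1.021 and 1.010 for rho 0.7, 0.8 and 0.9. The gain from substitution is small.

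**The case against.** The strongest reply is that substitution is implied. The outcome has to be swapped from FMMS to ARAT or gait velocity when the model is reused, and swapping its baseline is just as natural. Appendix I pairs a generic change outcome with a generic baseline term, which most readily means the baseline of the variable analysed. The SAP's own practice in the responder models and the NeuroQOL MMRM points the same way. Assistive device use has no counterpart in the FMMS model and had to be stated, so its mention does not show that everything else was to stay as listed.

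Much of this stands. It makes own-baseline intent plausible, but it does not settle the matter. The Appendix I code is a template that omits baseline mRS, which 9.1.2 requires, and assistive device use, which 9.2.3 requires. The SAP also uses baseline FMMS as a covariate for another outcome, the Global Rating of Perceived Change (9.2.5). That rating has no baseline of its own, but the precedent means baseline FMMS in an ARAT or gait model could not be dismissed as an obvious slip.

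A reader might infer more: that the SAP definitely prescribes the wrong covariate, that regression to the mean biases the comparison, or that two secondary endpoints are compromised. The documents do not support these. The wording is ambiguous. Under randomisation, regression to the mean is expected equally in each arm and enters the difference only through chance imbalance. The secondary endpoints for ARAT and gait velocity are responder proportions (SAP 4.2), and their GLMMs already name the own baseline. Nor are the subscales adjusted for an unrelated scale, since the total contains them.

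**Conclusion.** The point holds as a gap in specification. Read literally, the ARAT and gait velocity change MMRMs carry baseline FMMS total and do not name the baseline of the score analysed; Appendix I leans towards the own baseline without deciding it.

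The consequence of the literal reading is modest: about 2% to 15% more residual variance and intervals about 1% to 7% wider. Those figures rest wholly on the assumed ranges (rho 0.7 to 0.9, r 0.4 to 0.8), on equal variances, and on leaving baseline mRS out of the calculation. Chance imbalance in the own baseline would be only partly removed. Either model, fixed in advance, keeps its type I error.

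The analyses concerned are exploratory additions under SAP Section 12. The primary analysis and the protocol's secondary analyses are not touched. This is a worthwhile clarification and not a threat to the trial's conclusions.

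**What to change.** - **SAP 9.2.2 and 9.2.3:** state that the MMRM of Section 9.1.2 is used with baseline FMMS motor total score replaced by the baseline of the score analysed (affected-side ARAT, or gait velocity), keeping baseline mRS and, for gait, assistive device use.
- **SAP 9.1.2:** for consistency, say the same for UE-FMMS and LE-FMMS, where the gain is small.
- **Appendix I:** define the baseline term as the baseline of the variable analysed, and add baseline mRS to the code.

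If the authors want baseline FMMS kept alongside the own baseline, they should say so explicitly.

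The cost is a few lines of text before unblinding. The baseline values are already collected, and the ARAT and gait baselines are already used in the responder models. No subject is lost, because a change score cannot be formed without its own baseline.

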9.2.3. Gait Velocity

Gait Velocity is measured on a standard 10 m walk. Two trials will be tested. The average results from the two trials will be used for analysis. A single trial result will be used if the result of one of the two trials result is missing. If physical support is needed, the velocity will be set as missing. The proportion of SB623 treated subjects that improve at least 1 functional level (e.g. from <0.4 m/s to 0.4-0.8 m/s or from 0.4-0.8 m/s to >0.8 m/s) from baseline on Gait Velocity will be compared to sham-surgery controls at each time point using a similar GLMM model to the primary efficacy analysis. The GLMM model will include treatment (SB623 combined doses vs. sham surgical control), assistive device use (yes/no), visit, treatment-by-visit, baseline gait velocity score, baseline mRS score and pooled surgical site as fixed effects. The analysis will be repeated by the comparisons of each SB623 group versus sham control for each visit.

Summary tables for actual and change from baseline in gait velocity score will be provided. The mean change from baseline in gait velocity score will be analyzed using the same MMRM model as specified in Section 9.1.2 for FMMS will be provided as well with assistive device use (yes/no) included as a covariate. In addition, for each treatment group, a shift table of frequencies and percentages will be presented summarizing changes in walk time status (< 300 seconds vs. \geq 300 seconds) from Baseline to each post-baseline visit. McNemar's Test will be used to test the null hypothesis that the true probability of a walk time < 300 seconds is equal at Baseline and the post-baseline visit.

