18.2.1.2 Secondary Efficacy Analyses

Secondary analyses will evaluate a number of endpoints:

- The proportion of SB623 treated subjects (pooling both SB623 doses) that improve at least 1 point on the Modified Rankin Scale (mRS) will be analyzed at 6 months (from

Baseline) using a similar GLMM model to the primary efficacy analysis. The GLMM model will include treatment (SB623 combined doses vs. sham surgical control), mRS baseline score and pooled surgical site as fixed effects.

- The proportion of SB623 treated subjects (pooling both SB623 doses) that improve at least 6 points on the Action Research Arm Test will be compared to sham-surgery controls at 6 months (from Baseline) using a similar GLMM model to the primary efficacy analysis. The GLMM model will include treatment (SB623 combined doses vs. sham surgical control), ARAT baseline score and pooled surgical site as fixed effects.
- The proportion of SB623 treated subjects (pooling both SB623 doses) that improve at least 1 functional level on Gait Velocity will be compared to sham-surgery controls at 6 months (from Baseline) using a similar GLMM model to the primary efficacy analysis. The GLMM model will include treatment (SB623 combined doses vs. sham surgical control), Gait Velocity baseline score and pooled surgical site as fixed effects.
- The mean change in the two of the four NeuroQOL subdomain T scores of SB623 treated subjects (pooling both SB623 doses) will be compared to sham-surgery controls at 6 months (from Baseline) using a mixed model repeated measures model (MMRM). The two subdomains include:
 - Upper Extremity Function (Fine Motor ADL)
 - Lower Extremity Function (Mobility)

The MMRM model will include treatment, visit, pooled site, corresponding baseline subdomain T score, and the treatment-by-visit interactions. Restricted Maximum Likelihood Estimation procedure will be employed using an unstructured covariance matrix. Missing observations will not be imputed for this analysis.

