3.5. DETERMINATION OF SAMPLE SIZE

The sample size was estimated based on the primary efficacy endpoint, proportion of responders, which is defined as ≥ 10 points improvement from baseline on the Fugl-Meyer Motor Scale (FMMS) motor total score, at Month 6 Last Observation Carried Forward (LOCF). Based on the results of the Phase 1/2a study it was assumed that the responder rate was 33% for the SB623 treatment group.

Given high surgical placebo response rates, it was assumed that the responder rate in the surgical sham was 11.7% (i.e. 35% of the treatment responder rate). Assuming an 80% power, alpha level of 0.05 (two-tailed test), and 2:1 (pooled SB623 treatments: control) ratio of randomization, a sample size of 138 (92 subjects in treatment group and 46 subjects in control group) is required to detect this 21.3% difference in the proportion of responders. Based on a 10% upward adjustment to compensate for dropout subjects, a total of approximately 156 subjects (104 treatment and 52 controls) will be required.

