A GLMM model will be utilized using the mITT population as primary analysis. The GLMM model will have the outcome variable, FMMS responder (either \geq or $<$ 10 points improvement in FMMS), and independent variables of treatment, visit, treatment and visit interaction, and pooled surgical site as effects, and baseline FMMS motor total score and baseline mRS score as covariates. Treatment, visit, and pooled surgical site will be treated as categorical variables. Visit will be fitted as a repeated effect within subject. Link function will be set to logit and distribution to binary. An unstructured variance-covariance structure will be used. If this fails to converge then the following variance-covariance structures will be used based on the step-down order until model convergence is obtained: heterogeneous Toeplitz, heterogeneous autoregressive, heterogeneous compound symmetry, and then compound symmetry. The Kenward-Roger method will be used to estimate the denominator degrees of freedom. Adjusted odds ratios and 95% CIs for each visit will be presented for combined SB623 versus sham control. A separate analysis will be repeated for the comparisons of each SB623 group versus sham control for FMMS response. A forest plot of odds ratios and 95% CIs will be presented for individual/combined SB623 versus sham control. The results for Month 6 will be the primary interest.

For FMMS response, a supportive analysis will also be conducted based on the per protocol population using the same statistical method and following the same process for selection of variance-covariance structure.

A logistic regression analysis will be conducted by visit to include FMMS response as outcome variable, and independent variables of treatment and pooled surgical site as effects, and baseline FMMS motor total score and baseline mRS score as covariates. Odds ratios and 95% CIs will be reported for each visit.

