APPENDIX I SAMPLE SAS CODE IN STATISTICAL ANALYSIS

- 1) Binary endpoint by generalized linear mixed model:

```
proc glimmix data=dataset order=data;
class treatment visit subjid pooled_site;
model response(event='1')= treatment visit treatment *visit baseline pooled_site/ dist=binary
link=logit ddfm=KR OR;
random visit/subject=subjid residual type=xx;
lsmeans treatment*visit/pdiff cl;
run;
```

- 2) Linear mixed model for repeated measures:

```
proc mixed data=dataset;
class treatment visit subjid pooled_site;
model chg=treatment visit treatment*visit baseline pooled_site /ddfm=KR;
repeated visit/subject=subjid type=xx;
lsmeans treatment*visit/pdiff cl;
run;
```

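### Gait responder model: adjusting for the gain needed to reach the next level, instead of baseline velocity as one slope, would be a cheap power gain on a secondary endpoint

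*SAP*

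**What the plan says.** SAP 9.2.3 defines a gait responder as a subject who moves up "at least 1 functional level (e.g. from <0.4 m/s to 0.4-0.8 m/s or from 0.4-0.8 m/s to >0.8 m/s". The responder GLMM contains treatment, assistive device use, "visit, treatment-by-visit, baseline gait velocity score, baseline mRS score and pooled surgical site as fixed effects". Protocol 18.2.1.2 names the same baseline covariate: "Gait Velocity baseline score and pooled surgical site as fixed effects".

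Section 9.2.3 does not state the functional form of the baseline term. It does call the model similar to the primary one, and SAP 9.1.1 says of that model: "Treatment, visit, and pooled surgical site will be treated as categorical variables". The sample code agrees. The CLASS statement is "class treatment visit subjid pooled_site", and `baseline` then appears once in "model response(event='1')= treatment visit treatment *visit baseline pooled_site/ dist=binary". Baseline velocity is therefore a single linear slope on the logit scale. Neither document adds baseline functional level, distance to the next cut-point or a spline, and neither gives a rule for subjects who start above 0.8 m/s.

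SAP 9.2.3 also plans an MMRM on change in velocity as a continuous outcome.

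**The concern.** What predicts response here is how far the subject is from the next cut-point, not the velocity itself. A subject at 0.39 m/s needs 0.01 m/s. A subject at 0.40 m/s needs more than 0.40 m/s. A subject at 0.79 m/s again needs about 0.01 m/s. A subject above 0.8 m/s has no higher level to reach. The response probability is therefore a saw-tooth in baseline velocity, and one slope cannot follow it.

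The stake is efficiency on one secondary endpoint. Baseline velocity is collected and adjusted for, but in a form that may do little more than leaving it out. The trial was sized for FMMS response only, with about 52 sham subjects, so there is little precision to spare.

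**Working it through.** **1. The plan's own figure.** The documents give no power for gait. The FMMS figure in SAP 3.5 rests on 33% vs 11.7% and "Assuming an 80% power, alpha level of 0.05 (two-tailed test), and 2:1 (pooled SB623 treatments: control) ratio of randomization". With the pooled-variance formula, p̄ = (0.117 + 2×0.33)/3 = 0.259 and

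n(sham) = [1.960·√(1.5×0.259×0.741) + 0.842·√(0.117×0.883 + 0.33×0.67/2)]² / 0.213² = (1.052 + 0.389)² / 0.0454 ≈ 45.8, so 46.

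That gives 46 + 92 = 138, with power 80.2%. Then 46/0.9 rounds up to 52 per arm, and 3×52 = 156. Both figures reproduce.

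**2. Shape of the response curve.** Let g be the gain needed: 0.4 − b below 0.4 m/s, and 0.8 − b from 0.4 to 0.8 m/s. If change is normal with mean μ and SD σ, P(response) = 1 − Φ((g − μ)/σ). With assumed μ = 0.05 and σ = 0.12 m/s:

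| Baseline (m/s) | 0.10 | 0.30 | 0.39 | 0.40 | 0.65 | 0.79 |
|---|---|---|---|---|---|---|
| P(response) | 2% | 34% | 63% | 0.2% | 20% | 63% |

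The saw-tooth comes from the responder rule. Only its height depends on μ and σ.

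**3. Power, everyone at or below 0.8 m/s.** Assumed mean gain 0.10 vs 0.03 m/s. For SD 0.08 to 0.16: 94 vs 47 subjects (104 and 52 less 10%), single-visit logistic Wald test, 4,000 trials. For SD 0.20 and 0.25: 92 vs 46, likelihood-ratio test, 800 runs.

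| Baseline | SD of change | No covariate | Linear velocity | Gain needed |
|---|---|---|---|---|
| Uniform 0.1–0.8 | 0.08 | 52% | 54% | 74% |
| | 0.12 | 40% | 41% | 52% |
| | 0.16 | 31% | 32% | 37% |
| | 0.20 | – | 27% | 29% |
| | 0.25 | – | 22% | 23% |
| Truncated normal | 0.08 | – | 50% | 73% |
| | 0.12 | – | 39% | 52% |
| | 0.16 | – | 30% | 36% |

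Type I error was 3.7–4.9% for both terms.

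**4. Power when some subjects start above 0.8 m/s.** 92 vs 46, likelihood-ratio test, gamma baseline, SD of change 0.15, sham drift 0.03 m/s. The alternative here is gain needed plus an indicator for starting above 0.8.

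| Baseline mean/SD | Shift | No covariate | Linear | Alternative |
|---|---|---|---|---|
| 0.30/0.15 | 0.13 | 85% | 85% | 92% |
| 0.55/0.30 | 0.13 | 70% | 71% | 84% |
| 0.90/0.35 | 0.16 | 52% | 60% | 79% |
| 1.00/0.30 | 0.16 | 37% | 45% | 62% |

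The second row gives response rates of 17.0% vs 36.9%, close to the 20-point gait difference mentioned in Protocol Appendix A, 20.4. Adding simulated mRS and assistive device to that row gives 71% vs 83%. Its type I error is 5.3% (linear) and 5.9% (alternative), with simulation error about 0.5 point. Over all scenarios run, the linear term explained 0.1–6.0% of responder variance, against 11–36% available from baseline velocity. With baseline 0.75/0.35, SD 0.20 and a shift of 0.16, the gap was still about 9 points (63–65% vs 72–74%); part of that comes from separating out subjects above 0.8.

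**5. Repeated visits.** A five-visit marginal logistic model with treatment-by-visit, tested at Month 6, stood in for the planned GLMM (assumed within-subject correlation 0.7; 300 trials, error about 3 points). With the uniform baseline of step 3, no covariate/linear/gain needed gave 53/56/75% (SD 0.08), 41/42/52% (SD 0.12) and 27/30/35% (SD 0.16). Type I error at SD 0.12 was 5.7% (linear) and 4.7% (gain needed).

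**The case against.** The planned test is valid and its covariate is the one the protocol names. The MMRM in SAP 9.2.3 uses the continuous information that the dichotomy throws away, and a linear baseline suits it. Every power figure rests on assumed inputs, and the largest need a small SD of change. No simulation included pooled site, and all gave every subject the same expected gain, although Protocol Appendix A, 20.4 ties gait improvement to baseline immobility. Eligibility accepts an upper-limb or a lower-limb Motricity score and mRS 2, so fast walkers can enrol; in a fast cohort the linear term adds 8–9 points over no adjustment.

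Most of this stands, and it limits the point to efficiency. It does not remove it. The MMRM is a further analysis, while the secondary endpoint listed in SAP 4.2 is the responder proportion. In the fast cohorts the linear term still trails by 17–19 points. The repeated-visit check gave much the same gaps as the single-visit model.

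A reader might infer that the planned analysis is biased, or that a chance imbalance in near-threshold starters would make it misleading. The documents do not support this: assignment is randomized, such imbalance is already reflected in the test's error rate, and simulated type I error is near 5%. Nor do they support a claim that the linear term is worthless in any cohort.

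**Conclusion.** The point holds as a cheap improvement to one secondary endpoint; it does not show an error in the plan. The shape mismatch follows from the documents alone. Its cost does not. The direction was the same in every scenario run, but the gain ranged from about 1 to 20 points (23 in the most favourable case): roughly 11–23 points at SD 0.08–0.12, 5–6 at SD 0.16, and 1–2 at SD 0.20–0.25 for the modest effect in step 3, and more with larger assumed effects or a faster cohort. A reader might take a loss of about 20 points as established. It is not, because the documents give no baseline distribution, SD of change or expected gain for gait. The primary endpoint is unaffected.

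**What to change.** Before unblinding, amend SAP 9.2.3 as follows.

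- In the responder GLMM, replace baseline gait velocity with the gain needed to reach the next functional level: 0.4 minus baseline below 0.4 m/s, and 0.8 minus baseline from 0.4 to 0.8 m/s. Baseline level may be added. With level included, this is algebraically the same model as keeping baseline velocity and adding level, because gain needed is the level's cut-point minus velocity.
- State that subjects starting above 0.8 m/s have no higher level to reach. Count them as non-responders in the mITT descriptive proportions, and fit the odds-ratio model to subjects at or below 0.8 m/s. Without this sentence their covariate is undefined and they would drop out unannounced. A top-level indicator is equivalent in principle, but with no responders in that group it is quasi-separated and may not converge.
- Keep linear baseline velocity in the MMRM.
- Report the change from the protocol covariate under Protocol 18.8.

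The cost is a few sentences and one variable derived from data already collected. The odds ratio becomes conditional on a different covariate and applies to subjects able to improve a level, and there is a documented departure from the protocol.
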